## Approach to confounding

Physicians make treatment choices in light of available clinical information and as a result there is a risk of confounding by clinical indication for the treatments under study. Our design minimizes confounding by indication by focusing on diagnostic subgroups. To further reduce confounding, we will control for a broad range of potentially relevant factors from claims histories. These factors will be identified in the 365-day period before drug initiation and used to calculate propensity scores. In addition we will conduct sensitivity analyses to estimate the extent of unmeasured confounding necessary to fully explain our observed findings and we will conduct instrumental variable analyses if a suitable instrument is identified.

## Follow-up and censoring

Follow-up will begin at the date of new treatment initiation (t0 or index date) and will end after 365 days regardless of changes in pharmacotherapy (intent-to-treat approach). We will also conduct secondary analyses using a 180-day follow-up period and an as-treated specification. In the as-treated approach, follow-up will end at discontinuation of the new treatment ( $>10$  days without drug) or addition of another psychotropic agent (antipsychotic, mood stabilizer, antidepressant, or benzodiazepine). All analyses will be censored at loss of Medicaid (because that is the data source) with one exception—in intent-to-treat mortality analyses, follow-up will not be censored at loss of Medicaid because date of death data comes from the Social Security Master File, not Medicaid.

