### Subgroups

From the base study population described above, 5 clinical subgroups will be defined based on the presence of psychiatric diagnoses during the 30 days prior to and inclusive of the treatment change under study (index date) and who have this same diagnostic code from more than one provider to increase the validity of the diagnostic groups. The subgroups will be defined by codes to capture 1) uncomplicated schizophrenia (with schizophrenia codes from at least 2 different providers and without any diagnoses that would qualify them for the other subgroups during the 365 days prior to the index date), 2) schizoaffective disorder (ICD-9: 295.7) as the most recent schizophrenia-spectrum diagnosis, 3) depressive (ICD-9: 293.83, 296.2, 296.3, 296.9, 298.0, 300.4, 311), 4) manic (296.0, 296.4-296.8), and 5) anxiety (293.84, 300.00-300.02, 300.09, 300.20-300.23, 300.29, 300.3, 300.7, 308.0-308.9, 309.21, 309.81, 312.39, 313.0, 313.21, 313.23). These subgroups are defined to reflect the reason for the change in treatment.

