## Outcomes of interest

### Primary

The primary effectiveness outcome will be time to psychiatric hospitalization.

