### Secondary

We will also investigate time to index treatment discontinuation, time to introduction of another psychotropic medication, psychiatric emergency department visits, all-cause hospitalization, and death.

We will investigate adverse effects of medications including incidence of major cardiovascular events and diabetes mellitus.

Outcomes	
Death	Date of death will be defined by the Social Security Death Master File.
Psychiatric Hospitalization	Hospital claims will define inpatient admissions with a first listed mental disorder diagnosis (ICD-9:290-310). High levels of agreement between diagnoses in inpatient medical records and inpatient claims have been reported for several mental disorder groups, including schizophrenia (100.0%), major mood disorders (98.7%), alcohol dependence (97.8%), and drug dependence (96.4%). 
Psychiatric ED Visits	Emergency department claims are a reliable source of diagnostic information in relation to medical records and a valid source of illness severity information.  Emergency department visits in which the first listed diagnosis is a mental disorder (ICD-9-CM: 290-319) will be defined as emergency department mental health visits.
Self-Injurious Behavior	Deliberate self-harm will be defined by an E-code of E950-E958, excluding late effects of deliberate self-harm (E959), on any inpatient, emergency department, or outpatient claim. High positive predictive values have been reported. 
Diabetes Mellitus	One or more claims with a physician diagnosis of diabetes will define diabetes mellitus. Using self-reported diabetes status as the criterion standard, $\geq 1$ physician claim with any diagnosis of diabetes or a diabetes complication (ICD-9 codes: 295.00-2950.93, 357.2, 362.0-362.02, 366.41) has acceptable sensitivity (68.5%) and specificity (96.9%), and (kappa=0.76).  Sensitivity of 90% and specificity of 93% with self-reported diabetes. 
Cardiovascular Events:	Acute myocardial infarction (AMI) (ICD-9-CM: 410) or stroke (430-438, except 435) will be defined by diagnostic codes on inpatient claims of $\geq 3$ days in duration.  With this AMI definition 75% met criteria for definite or probable AMI on independent review of cardiac biomarkers, electrocardiograms, presenting symptoms, and medical history, and an additional 12% had a suspected AMI. 

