**Health care services, past year**

- Mental Health Emergency Service
- Outpatient visits for Schizophrenia (0-9, 10-29, 30-49, ≥50)
- Hospital admissions for psychiatric illness (1, 2, 3, ≥4)
- Psychotherapy
- Psychosocial Service contacts

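### Follow-up opens on t0, which is also a baseline day, so on a literal reading a psychiatric visit or admission dated t0 that prompted the new drug counts as an outcome and goes unadjusted

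*Combined protocol and SAP*

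**What the plan says.** Follow-up and censoring sets the time origin: "Follow-up will begin at the date of new treatment initiation (t0 or index date". Intent-to-treat follow-up then runs for 365 days.

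Subgroups places patients by psychiatric diagnoses recorded "during the 30 days prior to and inclusive of the treatment change under study (index date", and explains the purpose: "These subgroups are defined to reflect the reason for the change in treatment".

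Approach to confounding gives the covariate window: "These factors will be identified in the 365-day period before drug initiation and used to calculate propensity scores". Propensity score estimation and application likewise limits the score to predictors that precede treatment assignment. Appendix 2 lists past-year mental health emergency service and "Hospital admissions for psychiatric illness (1, 2, 3, ≥4" among the covariates.

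On outcomes, "The primary effectiveness outcome will be time to psychiatric hospitalization". The outcome table says "Hospital claims will define inpatient admissions with a first listed mental disorder diagnosis", and for emergency care "Emergency department visits in which the first listed diagnosis is a mental disorder (ICD-9-CM: 290-319) will be defined as emergency department mental health visits". Neither definition has a rule for events dated t0, for patients already in hospital on t0, or for which date fixes an admission. The Sensitivity Analyses section does not take up events on t0.

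**The concern.** One calendar day serves both as baseline and as follow-up. The cohort consists of people whose treatment changed because problems persisted, so some will have had a psychiatric crisis on the day the new drug was filled. Claims give dates and not times, so such an encounter cannot be placed before or after the fill. With follow-up opening on t0 and covariates closing before it, the encounter enters as a treatment failure and is missing from the propensity score. Yet the plan treats the same kind of encounter in the past year as a confounder.

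If one drug class is started from crisis encounters more often than another, the class with more t0 events looks worse from the first day. The outcomes exposed are psychiatric emergency visits, psychiatric hospitalization (the primary outcome) and all-cause hospitalization. Diabetes is exposed too, since a single claim dated t0 meets its definition.

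**Working it through.** **The windows side by side**

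| Window | Section | Does it include t0? |
|---|---|---|
| Subgroup diagnoses | Subgroups | Yes, explicitly |
| Propensity-score covariates | Approach to confounding; Propensity score estimation and application | Before initiation; t0 not stated to be included |
| Outcome follow-up | Follow-up and censoring | Yes, it starts there |
| Same-day exclusion for outcomes | Outcome table; Sensitivity Analyses | None |

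**The plan's own figure.** No stated number is in dispute. The one that bears on this outcome is the power claim in Sample size: 1,534 patients per group, a 5.0-point difference in one-year admission, at least 80% power. A pooled two-proportion test (two-sided 0.05) gives 0.800 at 40% v 45%, 0.913 at 20% v 25%, and 0.791 at the worst case of 47.5% v 52.5%. It reproduces, and power does not decide this point.

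**Illustration with no true effect.** All inputs here are assumed, because the documents give neither day-0 rates nor a baseline event rate. Let r be the one-year risk after t0, equal in both arms, and let a and b be the proportions with an event on t0.

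Cumulative-hazard ratio = ln[(1−a)(1−r)] / ln[(1−b)(1−r)]

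For r = 25%, a = 3%, b = 0.5%: (0.0305 + 0.2877) / (0.0050 + 0.2877) = 1.09.

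| r | 2% v 0.5% | 3% v 0.5% | 5% v 1% |
|---|---|---|---|
| 15% | 1.09 | 1.15 | 1.24 |
| 25% | 1.05 | 1.09 | 1.14 |
| 40% | 1.03 | 1.05 | 1.08 |

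With a = b the ratio is 1.00 in every row. A Cox estimate need not equal these ratios exactly.

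**Equal day-0 proportions with a true effect.** Each observed risk is q + (1−q) × risk, with q the common day-0 proportion. A true risk ratio of 0.80 (20% v 25%) becomes 0.2080/0.2575 = 0.81 at q = 1%, 0.2240/0.2725 = 0.82 at 3%, and 0.2400/0.2875 = 0.83 at 5%.

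**False-positive chance.** Take 1% v 3% on t0 and no true effect, so that the apparent one-year risks at r = 25% are 25.75% v 27.25%. With 1,534 per group, the chance of declaring the second arm worse is 0.24, 0.15 and 0.11 for r = 15%, 25% and 35%, against a nominal 0.025 in that direction. In the largest subgroup, 70% of 27,005 and of 12,248 episodes is about 18,900 and 8,570 patients. The same inputs at r = 25% give 0.74 (0.94 at r = 15%, 0.47 at r = 40%). This is unweighted; weighting would reduce the effective sample size.

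**The planned 180-day analysis.** If half the r = 25% cumulative hazard has accrued by then (0.2877/2 = 0.1438), the 3% v 0.5% ratio is (0.0305 + 0.1438)/(0.0050 + 0.1438) = 1.17 rather than 1.09, and the 5% v 1% ratio is 1.27 rather than 1.14. A shorter window gives t0 events more weight, so agreement between the 180-day and 365-day results would not be reassuring.

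**The case against.** The strongest reply is that the plan nowhere states that a same-day event is an outcome. It gives a time origin and event definitions and is silent on ordering within t0. That is correct: the counting follows from reading the sections literally together, and a programmer could do otherwise. It is still more than missing detail, because the start date is stated and nothing removes events that fall on it.

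Several stronger readings are tempting but not supported:

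- *Every triggering encounter is miscounted.* Only those dated exactly t0 are. Earlier ones lie before follow-up and inside the covariate window, unless admissions are dated by discharge or claim, which the plan leaves open.
- *A single t0 visit both assigns the subgroup and counts as the outcome.* Subgroups asks for the same code from at least two providers, so one visit generally cannot qualify a patient alone.
- *The t0 crisis is definitely outside the propensity score.* A visit that led to the prescription could be argued to precede assignment. The covariate window does not say that t0 is included.
- *Benzodiazepines are the class harmed.* This is conceivable, but the documents contain no data on it.
- *The primary outcome is shown to be biased.* An admission and a fill on the same date are needed, and nothing indicates how often that happens.

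The illustration also assumes unequal arms, so its range excludes 1.00 by construction. Finally, moving all t0 encounters to baseline can discard genuine post-fill events and adjust for something that followed treatment. That stands, and it is why a sensitivity analysis belongs with the change.

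**Conclusion.** The point holds in a limited form. The stated follow-up start, the baseline window that includes t0 and the pre-initiation covariate window together let a psychiatric encounter dated t0 enter as an unadjusted outcome, and no planned analysis tests for it. A false difference arises only if t0 events are unevenly spread across drug classes. Under the assumed unequal proportions the cumulative-hazard ratio is about 1.03 to 1.24. With equal proportions it is 1.00 under the null, and true effects are slightly diluted. Actual size and direction cannot be determined from the documents, least of all for the primary outcome. A reader might infer that the plan knowingly counts the trigger as a treatment failure, or that a particular comparison is biased; the text supports neither. The change is worth making because the subgroups are large enough for a small artefact to reach significance, and because a rule left unstated would be settled in programming.

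**What to change.** In Follow-up and censoring, start outcome ascertainment on t0+1 for every outcome except death. In the outcome table, date hospitalizations by admission date. In Approach to confounding and Appendix 2, treat psychiatric emergency visits and inpatient stays dated t0, including patients who are in hospital on t0, as baseline and enter them in the propensity score. In Sensitivity Analyses, add an analysis that counts t0 events as outcomes, and report the number of t0 events by treatment arm.

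The cost is a few sentences, a small number of covariates and one extra analysis, with no new data. The downside is that a few genuine post-fill events on t0 are lost, and some t0 covariates may be post-treatment because claims cannot order same-day events.

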## Analysis plan

**AIM 1 Comparative Effectiveness: Main Effects:** Within five clinically important schizophrenia subgroups, compare the effectiveness and safety of alternative medication strategies beyond antipsychotic monotherapy.

We will construct Cox models to estimate effects of the study treatments. We will first examine unadjusted treatment effects and then will conduct analyses using basic adjustment for demographic factors. Then we will construct Cox models using weighted propensity scores. Follow-up time will be censored at discontinuation or change of second drugs, death, or loss of Medicaid.

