### Sensitivity Analyses

We will conduct sensitivity analyses to confirm findings from the primary analyses and to examine their generalizability. In addition to the primary 360-day intention-to-treat analyses we will conduct 180-day intention-to-treat analyses and as-treated analyses. Another sensitivity analysis will examine subgroups of people with depression, anxiety, or mania diagnoses that are listed by more than one provider.

**Quantitative Sensitivity Analyses for Unmeasured Confounders.** Because the observed relative risk is a closed-form function of the balance of confounders among exposure groups, the strength of the confounder, and the prevalence of the confounder, it is possible to estimate the extent of unmeasured and thus unadjusted confounding necessary to fully explain the observed findings, i.e., would move the observed relative risk to statistical insignificance (the null).

To quantify how strong unmeasured confounding would have to be to explain the observed effect sizes among our comparison groups, we will use the array approach to understand how the strength of unmeasured confounders with known associations with our outcomes, such as BMI and risk of diabetes, and the confounder imbalance among study groups might affect the observed relative risk.

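### As-treated follow-up stops when the index drug is stopped or another psychotropic is added, with only baseline weights, so as-treated hazard ratios are open to informative-censoring bias; the 10-day gap also lacks a rule for inpatient days

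*Combined protocol and SAP*

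**What the plan says.** *Follow-up and censoring* makes the main analysis one in which follow-up "will end after 365 days regardless of changes in pharmacotherapy (intent-to-treat approach"). It then adds: "We will also conduct secondary analyses using a 180-day follow-up period and an as-treated specification". For that specification, "In the as-treated approach, follow-up will end at discontinuation of the new treatment", defined as more than 10 "days without drug) or addition of another psychotropic agent (antipsychotic, mood stabilizer, antidepressant, or benzodiazepine"). *Sensitivity Analyses* repeats the ranking, although with a different length: "In addition to the primary 360-day intention-to-treat analyses we will conduct 180-day intention-to-treat analyses and as-treated analyses".

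Under *Analysis plan*, Aim 1, the Cox models are described differently: "Follow-up time will be censored at discontinuation or change of second drugs, death, or loss of Medicaid". That sentence is not labelled as-treated or secondary.

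On adjustment, *Approach to confounding* says of the covariates: "These factors will be identified in the 365-day period before drug initiation and used to calculate propensity scores". *Propensity score estimation and application* names two kinds of weight, by the odds and by the inverse probability of treatment. Neither section, nor any other, mentions censoring weights or covariates measured after the index date.

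Stopping is also an outcome in its own right under *Secondary*: "We will also investigate time to index treatment discontinuation". No section says how inpatient days or carried-over supply count toward the gap.

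**The concern.** A Cox model that censors at stopping or adding assumes that, given the covariates used, patients who are censored have the same future risk as those who stay in follow-up. The plan gives reason to doubt this. *Data source and cohort identification* treats the index drug addition as a sign that the patient still has problems, so a further addition is likely to carry similar information. Baseline weights cannot correct for worsening that arises after the index date.

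Censoring linked to prognosis distorts a hazard ratio when it removes high-risk patients at different rates in the two arms. The arms are four drug classes, and the plan lists time to discontinuation and time to another psychotropic as outcomes to compare. Differences in stopping and adding are therefore a live possibility.

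What is at stake is the value of the check. The sensitivity analyses are meant to confirm the primary findings, and a distorted as-treated result could falsely support or contradict the intent-to-treat answer.

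**Working it through.** The plan states no figure for this point, so there is none to reproduce. All inputs below are assumptions chosen to show the range.

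**Mechanism.** Patients are stable or worsened. Worsening multiplies the admission hazard by *k*. If *p*(t) is the worsened share among those still followed, the ratio of hazards at time t when treatment has no effect is

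HR(t) = [1 + (*k* − 1)·*p*_B(t)] / [1 + (*k* − 1)·*p*_A(t)].

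It is 1 when *p*_A = *p*_B and departs from 1 when one arm loses worsened patients faster. The Cox estimate averages HR(t) over follow-up, weighted by events.

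**Daily model, 365 days.** Admission hazard 0.0005, worsening 0.003, true HR 1.

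| Multiplier on stop/add once worsened (A, B) | Base stop/add rate per day (A, B) | Cox HR, *k* = 2 | Cox HR, *k* = 3 |
|---|---|---|---|
| 1, 1 | 0.005, 0.005 or 0.005, 0.010 | 1.00 | 1.00 |
| 3, 3 | 0.005, 0.005 | 1.00 | 1.00 |
| 3, 3 | 0.005, 0.010 | 0.97 | 0.94 |
| 1, 3 | 0.005, 0.005 | 0.92 | 0.87 |
| 1, 3 | 0.005, 0.010 | 0.91 | 0.85 |

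Swapping the arm labels inverts each ratio (for example 1/0.87 = 1.15), so direction depends on which class loses worsened patients faster.

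**Weekly model, 52 weeks.** Admission hazard 0.005, *k* = 4, worsening 0.02, base stop/add rate 0.015 in A and 0.03 in B. Within each week the order is admission, then stop/add, then worsening. True HR 1.

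| Multiplier on stop/add once worsened (A, B) | Cox HR | Crude rate ratio |
|---|---|---|
| 1, 1 | 1.00 | 0.946 |
| 4, 4 | 0.916 | 0.883 |
| 1.5, 4 | 0.827 | 0.774 |
| 4, 1.5 | 1.085 | 1.055 |

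Hand check of the third row at week 26: *p*_A = 0.331 and *p*_B = 0.172, so HR(26) = (1 + 3 × 0.172)/(1 + 3 × 0.331) = 1.516/1.993 = 0.76. The ratio starts at 1, which is why the Cox average is milder. The Cox column is the relevant one because the plan uses Cox models. The first row shows that a crude rate ratio departs from 1 even when censoring carries no information.

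**Effect of censoring weights.** In the daily model, weights that use the true worsening state return 1.00 in every row. This is by construction, because worsening is fully observed there. A random simulation of the same model with 300,000 patients and untruncated true weights gave 1.07 and 0.95 (unweighted 0.92 and 0.84) in the last row of the first table, for *k* = 2 and 3. About 95% of arm B was censored there, so instability is a practical concern.

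**Scale.** If 20–40% of the reference arm were admitted in a year (assumed), a spurious HR of 0.85 would equal 0.20 − (1 − 0.80^0.85) = 2.7 points, up to 0.40 − (1 − 0.60^0.85) = 4.8 points. *Sample size* works with differences of 4 to 5 points in the larger comparisons.

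**Inpatient days under a fills-only reading.** Assume stay length is exponential with mean μ, remaining supply is uniform on 0–30 days, and nothing is filled during the stay. Then

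P(gap > 10 days) = e^(−10/μ) × (μ/30) × (1 − e^(−30/μ)).

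- μ = 7: 0.240 × 0.233 × 0.986 = 5.5%
- μ = 10: 0.368 × 0.333 × 0.950 = 11.7%
- μ = 14: 0.490 × 0.467 × 0.883 = 20.2%

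With 20–40% of patients admitted once a year, false discontinuations run from 0.20 × 5.5% = 11 to 0.40 × 20.2% = 81 per 1,000 patients who in fact persist.

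**The case against.** The strongest reply is that the as-treated analysis is secondary, one of several checks, and that intent-to-treat follow-up ignores drug changes. That stands, and it limits the weight of the point. It is also fair that reporting as-treated results with a stated limitation would be acceptable practice.

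A reader might infer four stronger things that the documents do not support:

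- **That as-treated hazard ratios are biased.** The tables give 1.00 when censoring is unrelated to worsening, and when dependence and base rates match across arms. No document supplies arm-specific rates, so the results are open to bias rather than shown to be biased.
- **That the plan counts inpatient days as days without drug.** It is silent. Filled prescriptions are named as the exposure source for the baseline monotherapy period only. The defect is a missing definition.
- **That inpatient gaps distort the as-treated hospitalization results.** The outcome admission is the event, and any gap it creates comes afterwards. Only an earlier non-psychiatric stay could censor the psychiatric outcome. The exposed results are time to discontinuation and as-treated death, cardiovascular, diabetes and emergency department outcomes.
- **That missing censoring weights bias time to discontinuation.** Stopping is the event there. Weights matter only if additions are treated as censoring, which the plan does not say.

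A reader might also take the Aim 1 sentence as proof that the main models use this censoring. Two other sections say the opposite, so it proves only a contradiction.

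**Conclusion.** The point holds as an inexpensive improvement to a secondary analysis. As-treated Cox models censor at events plausibly driven by worsening, and nothing planned handles worsening after baseline. Under assumed inputs and a true HR of 1, the estimate lies between 1.00 and about 0.83–0.92 or 1.08. These values rest on the assumed rates and multipliers, none of which the documents give, and the direction is unknown. The handling of inpatient days is a separate gap in definition.

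Under *Follow-up and censoring* and *Sensitivity Analyses* the intent-to-treat primary result is untouched. If the censoring sentence under Aim 1 governs instead, the same weakness reaches the main models. Settling that conflict matters more than the weights.

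**What to change.** 1. Reconcile the Aim 1 censoring sentence with *Follow-up and censoring* and *Sensitivity Analyses*, including the 365- versus 360-day difference, so that one rule clearly defines the primary analysis.
2. In the as-treated Cox models, add inverse-probability-of-censoring weights for stopping and for adding a drug. Use baseline covariates plus time-updated claims (emergency department visits, outpatient visits, other fills). Multiply by the treatment weights, truncate at a pre-specified point, and report beside the unweighted as-treated result.
3. State that inpatient days do not count toward the 10-day gap, in both the as-treated rule and the discontinuation outcome, and say how carried-over supply is treated. State whether an added drug censors time to discontinuation.

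The cost is SAP text and programming on data already held. The downsides are wider intervals, possibly unstable weights where few patients remain on the index drug, and only partial correction, because claims hold proxies for worsening.

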### Comparators

Pharmacological treatment options for patients with schizophrenia who are nonresponsive to antipsychotic monotherapy will include (1) initiation of a second antipsychotic, (2) initiation of an antidepressant, (3) initiation of a mood stabilizer and (4) initiation of a benzodiazepine.

Within each clinical subgroup, treatment options may be refined by exclusions at the drug class or individual agent level. For example, antidepressants are generally not considered treatment alternatives in patients presenting with mania, but could reasonably be considered for patients in the remaining four schizophrenia subgroups: depression, anxiety, schizoaffective disorder, and uncomplicated schizophrenia. Unless it is not considered a reasonable treatment option for a specific subgroup, initiation of a new antipsychotic will serve as the reference category because it is a frequently recommended approach to improving treatment response and is a common treatment strategy across all of the clinical subgroups under study. A survey on the prescribing behaviors of clinicians who prescribe psychotropic medications for individuals with schizophrenia will inform these choices.

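### Discontinuation rests on a single gap of more than 10 days for every drug class and fill size, with no other gap length planned, so late refills can be counted as stopping

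*Combined protocol and SAP*

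**What the plan says.** All references are to the combined protocol and SAP.

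- **Follow-up and censoring.** The main follow-up "will end after 365 days regardless of changes in pharmacotherapy (intent-to-treat approach"). The other specifications are secondary: "We will also conduct secondary analyses using a 180-day follow-up period and an as-treated specification". The as-treated rule reads: "In the as-treated approach, follow-up will end at discontinuation of the new treatment", with discontinuation taken as more than 10 days without drug, "or addition of another psychotropic agent (antipsychotic, mood stabilizer, antidepressant, or benzodiazepine").
- **Outcomes, Secondary.** "We will also investigate time to index treatment discontinuation, time to introduction of another psychotropic medication". The outcomes table gives no definition of discontinuation.
- **Comparators.** The strategies are "(1) initiation of a second antipsychotic, (2) initiation of an antidepressant, (3) initiation of a mood stabilizer and (4) initiation of a benzodiazepine". The gap is the same for all of them.
- **Data source and cohort identification.** Drug use is identified from filled prescriptions in Medicaid claims.
- **Sensitivity Analyses.** On follow-up, "we will conduct 180-day intention-to-treat analyses and as-treated analyses". No second gap length appears, and the plan does not say whether unused supply from an early refill is carried forward.
- **Analysis plan, Aim 1.** Follow-up in the Cox models is said to be censored when the added drug is stopped or changed. This conflicts with the intent-to-treat rule above.

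**The concern.** A claims record shows when a supply should have run out. It does not show whether the patient stopped. Under a short gap, a patient who collects the next fill 11 days late is recorded as a permanent stop, although treatment continues.

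A fixed gap also treats fill sizes unequally. For a patient taking the drug at a steady rate, the rule acts as an adherence cut-off that depends on the days' supply dispensed.

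Three things are at stake:

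- Two classes with the same true stopping but different refill habits can differ in time to discontinuation, and the difference could be read as better tolerability or effectiveness.
- As-treated follow-up is cut short in patients still on drug. This loses events and favours punctual refillers.
- With one gap length, a reader of the results cannot tell whether a difference reflects stopping or refill timing.

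**Working it through.** **Inputs.** From the documents: gap G = 10 days, horizon 365 days, four classes. The documents give no figure for refill delay, days' supply or true stopping, so there is no plan figure to reproduce. Everything else below is assumed.

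**1. Cut-off under steady use.** With days' supply d, a patient is recorded as stopped when adherence falls below d/(d + 10):
- 15-day fills: 15/25 = 60%
- 30-day fills: 30/40 = 75%
- 90-day fills: 90/100 = 90%

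**2. Continuing patients recorded as stopped.** Assume 30-day fills, no true stopping and independent exponential refill delays with mean m = 30 × (1/adherence − 1). The chance that one refill is more than 10 days late is p = exp(−10/m). About k = 355/(30 + m) refills fall due early enough to complete a gap by day 365. The approximate share is 1 − (1 − p)^k.

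| Mean adherence | m (days) | p | k | Formula | Simulation, 10-day gap | Simulation, 30-day gap |
|---|---|---|---|---|---|---|
| 95% | 1.58 | 0.0018 | 11.2 | 2.0% | 2% | about 0% |
| 92% | 2.61 | 0.0216 | 10.9 | 21% | 21% | about 0% |
| 90% | 3.33 | 0.0498 | 10.7 | 42% | 41% | 0.1% |
| 85% | 5.29 | 0.151 | 10.1 | 81% | 81% | 3% |

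The simulation used 200,000 patients per cell. Lognormal delays with the same means give 4%, 18%, 33% and 71% at 10 days.

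**3. Delays that differ between patients.** If each patient's mean delay is drawn from a gamma distribution (shape 0.5 to 1), the gradient flattens. The 10-day share is 12% to 14% at 95% adherence and 40% to 49% at 85%. With a 30-day gap the range is about 0.5% to 14%.

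**4. Spurious contrast between two arms.** Suppose both arms truly stop at 40% per year, with adherence of 92% in one and 85% in the other. As approximate yearly rates:
- true stopping: −ln(0.60) = 0.511
- late refills, 92% arm: −ln(1 − 0.208) = 0.233
- late refills, 85% arm: −ln(1 − 0.809) = 1.655
- ratio: (0.511 + 1.655)/(0.511 + 0.233) = 2.9

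Simulation gives 2.8 to 2.9. The ratio falls to about 2.1, 1.7 and 1.5 when true stopping is 60%, 80% and 90%. With patient-level variation it runs from about 1.6 (40% stopping) to 1.2 (90%). With a 30-day gap and independent delays it is about 1.0 to 1.1; at 40% stopping, (0.511 + 0.031)/0.511 = 1.06.

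**5. Fill size.** At 90% adherence under the 10-day gap, 15-, 30- and 90-day fills give 5%, 41% and 75% if the mean delay grows with the fill. If the mean delay is 3.33 days for every fill size, they give 63%, 41% and 14%. The order reverses.

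**6. Late refills as a share of recorded stops.** Let s be the true stopping probability per refill. The share is (1 − s)p/[s + (1 − s)p]. It runs from 2% (s = 30%, p = 1%) to 88% (s = 2%, p = 15%), and exceeds one half only when p(1 − s) > s.

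**The case against.** The strongest reply is that the size is entirely assumed. That stands. A reader might infer that these measures mostly record late refills, and the documents do not support it. Step 6 spans 2% to 88%. In the step 4 model with 40% yearly stopping, late refills are only about 30% of recorded stops in the 92% arm, against about 75% in the 85% arm. Nothing in the documents says that any two classes differ in adherence in this way.

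The following limits also stand:

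- A reader might conclude that long fills are the more exposed. Step 5 shows that this depends on how delay scales with fill size.
- The plan does not state that the 10-day rule defines the secondary outcome. That is an inference from the absence of any other definition.
- As-treated follow-up also ends when another psychotropic is added, which the gap does not affect.
- A short gap has a purpose: it limits the off-drug days counted as exposed. A 30-day gap is also one fixed length, with steady-use cut-offs of 30/60 = 50% and 90/120 = 75%. The documents give no reason to prefer it as the main rule.

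What the reply does not remove is that the result is sensitive to the gap length and the plan never varies it. The longer gap reduced mislabelling in every scenario run.

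**Conclusion.** The concern holds as a gap in definition and sensitivity analysis. One short fixed gap applies to all classes and fill sizes, the secondary outcome has no definition of its own, and no alternative is planned. Late refills can therefore count as stopping, to a degree that may differ between classes.

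Under the stated assumptions the mislabelled share is negligible to dominant, and a spurious rate ratio of about 1.2 to 2.9 is possible for a 92% versus 85% adherence contrast. These figures show sensitivity to the gap. They are not estimates for this cohort.

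A reader might also infer that the primary result is compromised. If the follow-up section governs, it is not: the 365-day intent-to-treat analysis does not use the gap, and only secondary analyses are affected. If the Aim 1 censoring sentence governs, the rule reaches the main Cox models. The two sections must be reconciled before the reach can be settled.

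**What to change.** 1. In the secondary outcomes, state that time to discontinuation uses the definition in the follow-up section, with unused supply from early refills carried forward.
2. In the sensitivity analyses, pre-specify repeats of the discontinuation and as-treated analyses with 30-day and 60-day gaps and with one gap scaled to days' supply. Fix the multiple in advance. For instance, a gap equal to the last fill's days' supply d puts the steady-use cut-off at d/(d + d) = 50% for every fill size.
3. Claim a difference between classes in discontinuation only if its direction holds across the 10-day and all the added versions.
4. Reconcile the censoring sentence under Aim 1 with the follow-up section.

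The cost is protocol wording and a few more runs of the same code on data already held. Longer gaps count some off-drug days as exposed, up to about 20 more per true stopper when moving from 10 to 30 days (30 − 10) and up to about 50 at 60 days (60 − 10). Keeping the 10-day version alongside shows how much this matters.
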